**Intensive Models of HCV Care for Injection Drug Users
PREVAIL Study**

Version Number: 1.0

01 September 2012

NCT Number: NCT01857245

Injection drug users (IDUs) constitute 60% of the approximately 5 million people in the U.S. infected with hepatitis C virus (HCV). HCV is the leading cause of liver failure and transplantation in the U.S., and mortality and health care costs due to HCV are expected to increase over the next two decades. Successful HCV treatment leading to sustained viral response (SVR) is associated with decreased progression of liver disease and increased survival, but to date successful treatment of IDUs has been limited.

Although past HCV therapies have been relatively ineffective in genotype-1 infected patients (the most common genotype in the U.S.), newer regimens are substantially improved. With the addition of direct-acting antiviral agents, HCV treatment delivered within large clinical trials leads to SVR or cure in over 90% of genotype-1 infected patients, compared to 45% with previous regimens. However, SVR rates are as low as 14% in real-world settings (pegylated interferon and ribavirin). Initial triple therapy HCV regimens were associated with increased dosing frequency (three times daily), pill burden (up to 20 pills daily), and side effects. Newer regimens such as fixed-dose ledipasvir and sofosbuvir are dosed once daily and have minimal side effects. Nevertheless, IDUs may still have lower adherence and high rates of treatment discontinuation, and many of those who fail to attain an SVR will develop drug resistance.

If HCV treatment continues to be delivered within current models of care, most IDUs will not only fail treatment and develop resistance, but may transmit drug resistant viruses to others, leading to new reservoirs of drug resistant virus. Though a growing number of studies now provide support for using interferon-based HCV treatment regimens in IDUs, none have determined the best model for delivering treatment, and this lack of data has contributed to physician reluctance to offer HCV treatment to IDUs. To reduce HCV prevalence, decrease HCV transmission leading to new infections, decrease mortality and health-care costs, and eliminate disparities in HCV-related care, effective HCV treatment must be provided to IDUs.

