B.10. Generalizability of mDOT and CGT approaches. IDUs are at the heart of the HCV epidemic, and the majority of all cases in the U.S. and other developed nations are related to illicit drug use. There are several reasons for initiating this research in the methadone treatment setting: (1) drug users must attend their methadone program frequently because methadone take-home doses are linked to absence of illicit drug use; (2) methadone treatment is a congregate setting in which patients are already present nearly daily to receive methadone; and (3) drug users may have particular difficulty adhering with HCV treatment, in part because the side effects of IFN mimic the symptoms of opiate withdrawal. If proven effective, our mDOT model could be applied in other programs that serve the approximately 180,000 HCV-infected methadone patients in the U.S.¹²⁴⁻¹²⁵ as well as in other settings in which drug users are present nearly daily (e.g. correctional facilities, homeless shelters, day treatment programs, and residential substance abuse settings). DOT can be extended in the community through nurses and community health workers.¹²⁶⁻¹²⁷ If proven effective, our CGT model could be applied to many diverse clinical settings in which patients are able to attend clinic once weekly.

C. INNOVATION

- First randomized trial to test innovative intervention strategies for providing HCV-care to IDUs in the U.S.
- Concurrent group treatment (CGT) is an innovative model of care allowing groups of patients to concurrently initiate HCV treatment, leading to informed and activated patient groups with enhanced social support and trust in the healthcare team.
- Adherence monitoring of blister packs with Medi-ic® technology allows us to combine a state of the art electronic adherence monitoring system with weekly blister packs.
- First study to provide data on factors associated with resistance to HCV direct-acting antiviral drugs in IDUs, and to define associations between adherence and development of resistance.
- Innovative techniques for modeling cost, including quality adjustment for treatment failure and development of resistant-virus.¹²⁸
- First study to evaluate cost effectiveness of HCV treatment in a methadone clinic in a randomized trial.

D. APPROACH

D.1. Preliminary Studies

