D.3. Setting: Einstein and Montefiore Division of Substance Abuse (DoSA). DoSA is a clinical, research, and teaching division of Einstein's Department of Psychiatry and Behavioral Sciences. DoSA operates a comprehensive substance abuse treatment program providing pharmacotherapy and related services to about 4200 adults (≥ 18 years) with current narcotic addiction (typically heroin). The primary focus is treatment of opiate dependence with methadone, and the average methadone pick-up schedule is 5 times per week. At present, DoSA operates 12 clinics in 5 Bronx communities. The treatment paradigm relies on integrating general and HCV- and HIV-related medical, substance abuse, and mental health services under one roof. Multiple RCTs have been conducted in DoSA. Both recruitment and research visits will occur at DoSA. With [name] (HCV Medical Director), [name] (DoSA Research Director), and [name] (DoSA Medical Director), participant recruitment and private office space for research visits will be ensured.

D.4. Participants. Most DoSA patients are Hispanic (59%) or black (24%), male (62%), and live under the federal poverty line (81%). Mean age is 47 years. Approximately 65% (n=2730) are HCV-infected, and 75% of those have chronic HCV (n=2048); 70% have genotype-1 (n=1434), and 80% of those are HIV-negative (n=1147). We anticipate 800 new admissions over the 3-year recruitment period, representing another 216 HCV-monoinfected genotype-1 patients.

Table 1. Inclusion and Exclusion Criteria (also see Human Subjects)

Inclusion Criteria	Exclusion Criteria

 HIV-negative Willing to receive HCV treatment on-site Initiating treatment with fixed dose (sofosbuvir and ledipasvir) Receiving methadone in clinic at least once per week Age 18 or older Able to provide informed consent English or Spanish speaking 	
 Pregnant or breast-feeding

D.5. Recruitment. Recruitment (as with other successful studies conducted in this setting)^{129,132,142} will be both active and passive; for active recruitment DoSA medical providers will inform genotype-1 HCV-infected subjects about the study and assist with referral, and for passive recruitment subjects will self-refer. Self-referred subjects will meet with their provider to determine whether starting HCV treatment is appropriate.

Determination of eligibility.

Initial screening visit and informed consent:

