groups of approximately equal size. Because of the historical importance of IL28B genotype and stage of liver disease (cirrhosis v. no cirrhosis) in determining virologic outcomes,⁴⁶ we will stratify by these 2 factors. All subjects will have the IL28B genetic test performed as per our standard clinical algorithm. To determine presence of cirrhosis, all subjects will have 2 biomarker tests (APRI and Fibrosure) performed at baseline,¹⁴³⁻¹⁴⁴ per our standard clinical algorithm (Appendices A and D). Liver biopsy / Fibroscan is not required but will be performed if 1) biomarker tests are inconclusive for determination of cirrhosis as per the SAFE algorithm (<20%),¹⁴⁵ 2) to rule out co-occurring liver disease, or 3) if the result will influence the decision to initiate treatment. Results of liver biopsy / Fibroscan (if done) will be used for stratification instead of biomarker tests. Since IL28B explains much of the variability in response between African Americans and non-African Americans,^{96,146} and rates of SVR with DAAs may be equivalent in Latinos and non-Latino Whites,⁴⁶ we will not stratify by race or ethnicity, but will adjust in the analyses if necessary.

D.8. Treatment arms: TAU, mDOT, and CGT. All 3 models of care include co-located on-site care including HCV care, primary care, and substance abuse treatment. Table 2 summarizes similarities and differences between the 3 models. Subjects randomized to TAU will receive all medications monthly at the clinic from the clinic nurse, packaged in 7-day blister packs (oral medications)

Table 2: Element	IMB Model	TAU	mDOT	CGT
Co-located care	Information Motivation	X	X	X
Enhanced social support by providers	Motivation		Nurse – individual	Medical provider - group
DOT Interferon	Behavioral Skills		Nurse - individual	Medical provider - group
DOT telaprevir and ribavirin	Behavioral Skills		DAA 1-6 doses/week	
DOT snack (if telaprevir or RBV only)	Behavioral Skills		Nurse - individual	
Enhanced social support by patients	Motivation			Peers – group
Enhanced education	Information			Weekly educational sessions
Enhanced side effect management	Information Motivation		Nurse - individual	Weekly group treatment

D.8.1. Intensive treatment intervention arms (mDOT and CGT)

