Modified directly observed treatment (mDOT). Since DOT of HCV medications will be linked to methadone visits, the number of directly observed oral doses will vary based on the number of days the patients attends the clinic to receive directly observed methadone (pick-up schedule). This intervention is considered modified DOT (mDOT) since only 1-6 out of up to 24 weekly oral medication doses will be observed. Subjects in the mDOT arm will receive: 1) 1 to 6 directly observed oral medication doses per week at the same time as they receive methadone, and 2) individually packaged take-home doses for self-administration on days not in the clinic. In addition, methadone clinic nurses will: 3) notify clinicians when doses are declined, 4) assess for side effects using a standard script; and 5) refer subjects to onsite clinicians as necessary. Since some medications must be taken with food, subjects will also be provided with a high-fat snack (20 grams of fat) when necessary.

Concurrent group treatment (CGT). We developed this model by adapting models linking HCV support groups with treatment^{70,77-78} and models of group medical visits across many chronic conditions.¹⁸⁰⁻¹⁸² Weekly CGT meetings will have 6 components: 1) brief physical exams; 2) psychosocial support from peers and providers; 3) education; 4) direct administration of pegylated interferon medication in the group setting (if applicable); 5) side effect management; and 6) closing meditation on positive health. Six to 12 patients will receive treatment concurrently. Other intervention elements will be as follows.

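### Methadone pick-up schedule sets how much of mDOT a participant receives, yet the Aim 1 analyses do not name it as a covariate and no analysis by observed-dose intensity is planned

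*Combined protocol and SAP*

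**What the plan says.** **Entry and delivery.** Table 1 (D.4) requires "Receiving methadone in clinic at least once per week" and treatment with fixed-dose sofosbuvir and ledipasvir. The opening summary states: "Newer regimens such as fixed-dose ledipasvir and sofosbuvir are dosed once daily". Under D.8.1, "the number of directly observed oral doses will vary based on the number of days the patients attends the clinic", and mDOT participants receive "1 to 6 directly observed oral medication doses per week at the same time as they receive methadone". The same section explains the label *modified* by saying that "only 1-6 out of up to 24 weekly oral medication doses will be observed". D.3 reports that "the average methadone pick-up schedule is 5 times per week".

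**Link to drug use and adherence.** B.10 says that "methadone take-home doses are linked to absence of illicit drug use". B.6 says active drug use has been associated with nonadherence. D.1.6 reports, from the team's HIV trial, that drug use lowered adherence and that DOT removed this effect.

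**Randomization and analysis.** D.7 stratifies by IL28B genotype and cirrhosis. The balance variables named as examples in D.11 include active drug use but not pick-up schedule. Table 3 lists methadone dose and withdrawal scales, not pick-up frequency. The D.5 chart review abstracts clinic attendance, but no use in randomization or analysis is stated. D.11 brings unequally distributed variables into the models, and D.12.2 uses multivariable logistic regression if such variables are identified. The D.12.2 repeated-measures adherence model is to include potential confounders, which it does not name.

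**The concern.** B.10 justifies mDOT by near-daily attendance at the methadone program and describes once-weekly attendance as enough for CGT. The entry floor is nevertheless once a week for every arm. A characteristic fixed before randomization therefore decides whether an mDOT participant has most doses observed or almost none.

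Two consequences follow. First, a variable that is plausibly related to adherence enters the comparisons of proportions only if an imbalance is noticed, and no threshold for imbalance is given. Second, if mDOT shows no advantage over TAU, the planned output would not tell the reader whether observation failed to help or was barely delivered to part of the arm.

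**Working it through.** **1. Observed share of doses.** D.8.1's own figure is 1 to 6 of up to 24 weekly doses: 1/24 = 4% to 6/24 = 25%. With once-daily dosing there are 7 doses a week:

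| Pick-ups per week | Share observed |
|---|---|
| 1 (Table 1 minimum) | 1/7 = 14% |
| 5 (clinic average, D.3) | 5/7 = 71% |
| 6 (D.8.1 maximum) | 6/7 = 86% |

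The range within the arm is six-fold on either denominator. The wording *up to 24* is an upper bound, but it does not describe the regimen that Table 1 requires.

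**2. How many could attend once a week.** The documents do not say. Suppose enrolled patients share the clinic mean of 5 and nobody exceeds 6. The largest possible once-weekly share f solves 1·f + 6·(1 − f) = 5, so f = 1/5 = 20%, and everyone else must then attend 6 times.

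**3. Does the range reduce planned power?** Start from D.13's adherence figure: 80%, 80% and 50%, with 40 completers per arm.
- Mean proportion 0.70; noncentrality = 40 × (0.01 + 0.01 + 0.04)/(0.70 × 0.30) = 11.43.
- Power of the 2-df chi-square test is 86.65%, against the stated figure of more than 87%. The omnibus alpha of 0.05 is my assumption, as the plan does not state it.
- Pairwise mDOT versus TAU at two-sided 0.025, normal approximation: 72.6%.

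Now assume the 30-point gain scales with observed doses relative to 5 a week, so a participant with k pick-ups gains 30 × k/5 points. The average gain is 30 × (mean of k)/5. At a mean of 5 that is 30 points, whatever the spread. The mDOT rate stays at 80% and both power figures are unchanged.

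**4. Chance imbalance.** Assume a fraction f of patients attends once weekly, with two arms of 50 and no stratification on this factor. The probability that the arms differ by 10 percentage points or more (5 participants) is 0.13 at f = 10% and 0.26 at f = 20%.

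Would a check notice it? Take 10/50 versus 15/50 as an illustration. Chi-square = 100 × (10 × 35 − 15 × 40)² / (50 × 50 × 25 × 75) = 1.33 on 1 df, p = 0.25. A balance test would probably pass over a gap of this size.

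**5. Room for a covariate.** In the adherence models there is enough. For SVR it depends on failures. D.13's rates of 70%, 70% and 40% in 40 per arm give 12 + 12 + 24 = 48 failures. If SVR is above 95%, as B.3 and D.9.6 report for ledipasvir/sofosbuvir, the 100 participants on it would have fewer than 100 × 0.05 = 5.

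**The case against.** The best defence is that the protocol openly calls the intervention modified, ties observation to attendance, and adds side-effect assessment, notification of declined doses and referral. Intention-to-treat estimates that package as delivered, and randomization protects it from systematic bias. This stands: the range of observation does not invalidate the comparison.

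The plan also has partial safeguards. The D.11 list is illustrative, active drug use is on it, and imbalanced variables are adjusted for. Observed doses in the mDOT arm come from separate packs (D.10.4), so delivery can be measured. These points narrow the gap. But drug use is only a proxy for observation intensity, and data that could be analysed are not a planned analysis.

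Three stronger readings are tempting, and the documents do not support them.

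- **Loss of power.** A reader might scale down the benefit for once-weekly attenders while holding everyone else at 5 pick-ups. That pulls the mean below the 5 reported in D.3. With the mean kept at 5, linear scaling loses nothing. D.13's 80% also rests on pilot data in methadone patients, where 81% of mDOT participants reached the threshold (D.1.4), so whatever attendance variation that pilot had is already included.
- **Bias in SVR.** That pick-up schedule is prognostic is an inference from B.10 and B.6; no section reports it directly. D.1.3 found no association between illicit drug use and virological outcomes. The same chain suggests that infrequent attenders use fewer drugs and may need observation less.
- **Replacing IL28B as a stratifier.** D.7's phrase "historical importance of IL28B genotype and stage of liver disease" covers cirrhosis too. B.5's remark on ledipasvir/sofosbuvir concerns race and ethnicity, not IL28B. About 50 of the 150 participants are outside that regimen group, and a mid-trial swap would leave two stratification schemes in one analysis.

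**Conclusion.** The concern holds as a gap in the analysis plan. On the regimen Table 1 requires, mDOT may observe anywhere from 14% to 86% of doses. The variable that decides this is known before randomization and collected at screening, but no analysis names it. Waiting for a visible imbalance is a weak rule for such a variable.

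The size of the problem cannot be fixed from the documents, because the distribution of pick-up schedules is not given. If enrolled patients resemble the clinic average, once-weekly attenders are at most 20% and may be far fewer. Average power is affected only if enrolled patients attend less often than that average or the benefit is not proportional to observation; the documents show neither. The relation of schedule to adherence is plausible rather than demonstrated. This is a low-cost improvement in precision and interpretability, not a correction of an invalid comparison.

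**What to change.** 1. **D.12.2, covariate.** Name baseline methadone pick-up schedule, as abstracted at screening, as a covariate in the Aim 1 adherence models regardless of observed imbalance. Include it in the completion and SVR models where event numbers allow, with the rule for that written beforehand.
2. **D.12.2, reporting.** Add a secondary descriptive analysis of the mDOT versus TAU effect by baseline pick-up schedule, with the proportion of doses actually observed in each group. Compare arms within schedule groups. A comparison inside the mDOT arm by doses observed would mix observation with the drug-use history that earns take-home doses.
3. **D.8.1.** Reconcile the weekly dose count with the once-daily regimen in Table 1, so that the denominator for the observed proportion is clear for each regimen in the analysis.

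The entry criterion and the stratification stay as they are. The cost is analysis wording and one extra table. The baseline value is already collected, and the observed proportion can be derived from the separate packs; no patients or procedures are added. The schedule groups will be small, so item 2 should be labelled descriptive and carry confidence intervals.

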
 Obtain oral consent for brief screening using Einstein Committee on Clinical Investigations (IRB) screening consent template Brief screen in private room in methadone clinic to determine eligibility Discuss study procedures, risks and benefits of study participation Obtain written consent for 1) clinical trial participation; 2) study staff to use protected health information from methadone clinic records; 3) study staff to disclose protected health information in event of psychiatric distress
Methadone clinic chart review:

 Laboratory test results: HCV Ab, HCV viral load, HIV (within 1 year), HCV genotype/subtype, IL28B, APRI and FibroSURE (biomarker tests for liver fibrosis) Methadone clinic attendance and dose
Second screening visit (medical eligibility determination by [name]):

 Review of HCV-related labs (as above) and fibroscan or liver biopsy (if available) Review of HCV Treatment Evaluation Flow Sheet to confirm no previous HCV treatment and planned on-site treatment regimen: fixed dose (sofosbuvir and ledipasvir) Participants who meet all eligibility criteria scheduled for a baseline visit Randomization (stratified, blocked) generated by centralized computer program

D.6. Participant tracking and retention. We have extensive experience following HCV- and HIV-infected drug users in studies. In our ongoing RCT of directly observed HCV treatment, 24 week follow-up was 92%.¹²⁹ In our completed RCT of directly observed HAART, 24-week follow-up was 86%.¹⁴² At enrollment and subsequent visits, we will record: 1) participants' address, phone number, and social security number; 2) contact information of family or friends; 3) contact information of participants' community-based organizations; 4) contact information of case managers; and 5) locations where participants "hang out".

D.7. Randomization. We will recruit 150 patients (100 on fixed-dose sofosbuvir and ledipasvir), with patients randomized to mDOT, CGT, or TAU in a 1:1:1 ratio (50 subjects in each group) in variable block sizes of 3-6 via central, computer-generated randomization. Two special randomization strategies (stratification and blocking) will be used to avert imbalances in prognostic factors, and to ensure comparison

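### In a three-arm 1:1:1 trial, block sizes of 3-6 can only be 3 or 6, so staff who track a stratum could foresee about 20% to 33% of allocations with at least 75% certainty

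*Combined protocol and SAP*

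**What the plan says.** Section D.7 plans 150 patients in three arms, in a "1:1:1 ratio (50 subjects in each group) in variable block sizes of 3-6 via central, computer-generated randomization". It names IL28B genotype and cirrhosis status as prognostic and adds that "we will stratify by these 2 factors". The sizes of the resulting strata are not given, nor is the relative frequency of the block sizes. Nothing says that the sizes are withheld from the staff who recruit, assess eligibility or treat.

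The eligibility steps under D.5 run in this order: consent, chart review, a medical eligibility determination, scheduling of the baseline visit, and last "Randomization (stratified, blocked) generated by centralized computer program". The determination includes "Review of HCV-related labs (as above) and fibroscan or liver biopsy (if available)". The laboratory results it refers back to are IL28B, APRI and FibroSURE, which define the strata. D.5 also has medical providers inform and refer patients, and for self-referred patients the provider judges whether starting treatment is suitable.

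The plan does not use the term open-label. But sections D.8 and D.8.1 describe observed dosing at the methadone window (mDOT), weekly groups run by medical providers (CGT) and monthly packs from the clinic nurse (TAU). None of these can be hidden from staff.

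**The concern.** Central generation keeps the list hidden. It does not prevent inference from assignments already seen when the block sizes are small and known. Blocks of 3 are the worst case: once two arms have appeared, the third follows. Decisions on whom to refer, whether treatment is suitable and when to enter a patient come before assignment. If the next arm can be guessed, more reliable patients could be steered towards or away from an arm, perhaps without intent.

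Adherence, completion and SVR can all depend on reliability and motivation, and stratifying on IL28B and cirrhosis does not protect against selection on these. Section D.1.5 raises the same worry about the non-randomized CGT pilot, whose patients may have been more motivated. The variables that D.11 names for the baseline comparison do not include motivation, so a difference of this kind could pass unnoticed.

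**Working it through.** **Inputs from the plan.** Three arms, 1:1:1, 150 patients, block sizes 3-6 (D.7); two stratification factors (D.7). The plan's own figure reproduces: 150 / 3 = 50 per arm. The plan gives no predictability figure to compare with.

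**Assumptions.** Each block is drawn independently with a fixed mix of sizes, and the mix is varied below. Strata are either one stream of 150 or four strata of 38, 12, 75 and 25. The observer knows the possible sizes and every earlier allocation in the stratum, but is not shown where later blocks begin.

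**Step 1: possible sizes.** A block with equal numbers in three arms has size 3k. Of 3, 4, 5 and 6, only 3 and 6 qualify.

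**Step 2: one case by hand.** Take an equal mix and a block whose start is known (for example the first block in a stratum). The first two patients are in different arms with probability 1 in a block of 3 and 4/5 in a block of 6.
- P(size 3 | first two differ) = 0.5 / (0.5 + 0.5 × 0.8) = 0.556.
- P(third patient in the remaining arm) = 0.556 × 1 + 0.444 × 0.5 = 0.778.

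**Step 3: limiting cases by hand.**
- All 3s: the last of every three is certain, so 1/3 = 33.3%.
- All 6s: the sixth is always certain. The fifth is certain when the last two share an arm, which has probability 1/5. So (1 + 1/5) / 6 = 20.0%. No other position reaches 75%.

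**Step 4: mixed sizes.** Simulated sequences with exact Bayesian updating of the current block size and contents give:

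| Mix of 3s to 6s | Callable at ≥75%, one stream / four strata | Best guess right, one stream / four strata |
|---|---|---|
| 2:1 | 33% / 33% | 59% / 58% |
| 1:1 | 33% / 33% | 58% / 57% |
| 1:2 | 26% / 24% | 57% / 56% |
| 1:3 | 21% / 20% | 57% / 56% |
| all 6s | 20% / 19% | 56% / 55% |

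Chance is 1/3. At the equal mix in one stream, about 9% of allocations are fully certain, and calls made at ≥75% are right 87% of the time.

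**Step 5: weaker observers, equal mix.** Someone who ignores the strata and guesses the least-used arm is right about 46% of the time. If one same-stratum patient is randomized between the decision and the allocation, the share callable at ≥75% falls from about 32% to about 2% (stratum of 38).

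**Step 6: alternatives, sizes equally likely, one stream / four strata.**
- 6 and 9: 18% / 17% callable; best guess right 54% / 53%.
- 6, 9 and 12: 13% / 11% callable; best guess right 53% / 52%.

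**The case against.** The strongest reply is that these percentages describe an ideal observer. Section D.3 describes 12 clinics, D.7 implies at least four strata, and no section says that anyone logs the order of assignments within a stratum. The provider who judges suitability (a step stated for self-referred patients) need not be the reviewer who sees the stratum results, and the criteria in Table 1 are mostly objective. Eligibility is also settled before the baseline visit, so other patients may be pending. All of this stands. It limits how far the opportunity can be used, but does not remove it: the reviewer holds the stratum results and the arms are visible.

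A reader might infer that one third of allocations simply are predictable. The plan does not support that as a single figure. The mix of sizes is unstated, the share is about 20% if 6s predominate, and every figure in the table needs within-stratum tracking. The 78% case also needs a known block start.

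A reader might also attach a bias in percentage points. If guessing shifted patients' chance of success by an assumed 20 points, a fully informed observer would bias the TAU contrast by 0.36 × 20 = 7 points under 3/6, and by 0.28 × 20 = about 5.5 points under 6/9/12. With strata ignored it would be 0.19 × 20 = about 4 points under 3/6. The 20 points have no basis in the documents and fit poorly with the SVR above 95% cited in B.3 and D.9.6 for the current regimen. The comparison does show that larger blocks alone bring a modest gain.

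Larger blocks are also not better in every situation. With one intervening same-stratum patient, 6/9/12 is slightly easier to guess than 3/6 (about 3% against 2% callable; best guess 45% against 42-43%), although both are low.

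**Conclusion.** The point holds as a low-cost improvement, not as a flaw that invalidates the design. As written, the size range can only mean blocks of 3 or 6, and it is printed where enrolling staff can read it. For an observer with full knowledge of the stratum, about 20% (mostly or all 6s) to 33% (equal mix) of allocations could be called with at least 75% certainty. Best guesses would be right about 56-57% of the time (55-58% across the layouts tried, from an equal mix to all 6s).

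The result rests on the assumed mix, the assumed strata and complete tracking of earlier assignments. The documents show neither that such tracking takes place nor that enrolment has been selective, and any bias in points is illustrative only.

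**What to change.** For remaining enrolment (D.9.6 refers to newly enrolled subjects):

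1. Replace the 3-6 range in D.7 with randomly varied larger multiples of 3 and no block of 3, for example 6, 9 and 12.
2. State in the protocol only that blocks are of varying size. Hold the sizes in a restricted randomization document unavailable to recruiting and eligibility staff.
3. D.5 already lists the eligibility decision before randomization. Add that it is recorded and cannot be changed before the program is called, so that the order becomes a control.

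The cost is one program setting and a few lines of text. The statistical downside is slightly larger possible arm imbalance where a stratum ends mid-block. In an assumed stratum of 12, the mean gap between the largest and smallest arm rises from about 0.4 to about 0.8 patients. That should be judged stratum by stratum, not against the total of 150, but it is small.
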